
Section	Original Text	Revised Text
Section 16.2 Ethical Conduct of the Trial	The trial will be performed in accordance with ethical principles that have their origin in the Declaration of Helsinki ( <del>Seoul Revision, 2008</del> ) and are consistent with ICH/GCP, applicable regulatory requirements.	The trial will be performed in accordance with ethical principles that have their origin in the Declaration of Helsinki ( 64th WMA General Assembly, Fortaleza, Brazil, October 2013 ) and are consistent with ICH/GCP, applicable regulatory requirements.
Section 17.1 AE Reporting	The Investigator is responsible for recording AEs reported by the subject or discovered by any other means during the trial. In agreeing to the provisions of this protocol, the <del>investigator</del> accepts all legal responsibilities for immediate reporting of SAEs to <del>the Medical Monitor</del> .	The Investigator is responsible for recording AEs reported by the subject or discovered by any other means during the trial. In agreeing to the provisions of this protocol, the Investigator accepts all legal responsibilities for immediate reporting of SAEs to the Sponsor .
Section 18 Publication Policy	The Sponsor intends to publish the results of all of the clinical trials that it sponsors consistent with the Declaration of Helsinki ( <del>Seoul Revision 2008, [http://www.wma.net/en/30publications/10policies/b3/index.html, accessed May 22, 2013]</del> ). Consistent with the recommendations of the editors of several leading medical journals, the International Committee of Medical Journal Editors (ICMJE), authorship of publications resulting from Intercept sponsored studies should fairly recognize the activities of those that have made a significant contribution to the trial ( http://www.icmje.org/ethical_1author.html , accessed May 22, 2013). Thus, it is anticipated that authorship will reflect the contribution made by the Sponsor personnel, the Investigators, and others involved, such as statisticians.	The Sponsor intends to publish the results of all of the clinical trials that it sponsors consistent with the Declaration of Helsinki ( 64th WMA General Assembly, Fortaleza, Brazil, October 2013 ). Consistent with the recommendations of the editors of several leading medical journals, the International Committee of Medical Journal Editors (ICMJE), authorship of publications resulting from Intercept sponsored studies should fairly recognize the activities of those that have made a significant contribution to the trial ( http://www.icmje.org/ethical_1author.html , accessed May 22, 2013). Thus, it is anticipated that authorship will reflect the contribution made by the Sponsor personnel, the Investigators, and others involved, such as statisticians.

Section	Original Text	Revised Text
Section 19 List of References	
<del>Vairappan B. Modulation of the DDAH-ADMA pathway with the farnesoid X receptor (FXR) agonist INT-747 restores hepatic eNOS activity and lowers portal pressure in cirrhotic rats. Hepatology. 2009;50(4 Supplement):336A-7A.</del>
	
Chapman R. Primary sclerosing cholangitis. Autoimmune Liver Disease. 2011; 39(10):558-591.
 

Appendix A List of Planned Laboratory Analytes	
Hematology
 
<del>prothrombin time (PT and INR)</del>
 
<del>partial thromboplastin time (PTT)</del>
	
Coagulation Parameters
 
prothrombin time (PT and INR)
 
partial thromboplastin time (PTT)

## **APPENDIX I. PROTOCOL VERSION 4 – SUMMARY OF CHANGES**

**Background:** Protocol 747-207 has been prepared as a Phase 2 trial to evaluate the potential clinical benefit of obeticholic acid (OCA) in PSC.

**Rationale:** Version 4 of the protocol includes changes to clarify eligibility criteria.

**Summary of Changes:** The following revisions were made to the Protocol Version 3 in Protocol Version 4. (Note: Deletions are stricken and additions are indicated in bold font.) Minor grammatical changes are not detailed unless included with other changes (eg, capitalizations, punctuation).

Section	Original Text (Version 3)	Revised Text (Version 4)
Title Page	Original Version: 06 Jun 2014 Version 2: 24 September 2014 Version 3: 26 August 2015	Original Version: 06 Jun 2014 Version 2: 24 September 2014 Version 3: 26 August 2015 Version 4: 08 February 2016
Synopsis, ExclusionCriterion #5	Clinical evidence of dominant stricture ( <del>as evidenced by cholangiography or other appropriate imaging modality within the 12 months prior to Day 0) or current biliary stent</del>	Current clinical evidence of dominant strictures that are considered clinically relevant in the opinion of the Investigator or current biliary stent at Screening
Synopsis, ExclusionCriterion #6	Current cholecystitis <del>or gallstones (identified by hepatic imaging)</del>	Current cholecystitis or evidence of current biliary obstruction due to gallstones. Asymptomatic gallstones that are not considered a safety risk in the opinion of the Investigator might be acceptable subject to discussion and agreement with the Medical Monitor
Synopsis, ExclusionCriterion #10	Known Gilbert’s syndrome or elevations in unconjugated (indirect) bilirubin >ULN	Known Gilbert’s syndrome or history of elevations in unconjugated (indirect) bilirubin >ULN or unconjugated (indirect) bilirubin >ULN at Screening
8.3. Subject Exclusion Criteria, ExclusionCriterion #5	Clinical evidence of dominant stricture ( <del>as evidenced by cholangiography or other appropriate imaging modality within the 12 months prior to Day 0) or current biliary stent</del>	Current clinical evidence of dominant strictures that are considered clinically relevant in the opinion of the Investigator or current biliary stent at Screening
8.3. Subject Exclusion Criteria, ExclusionCriterion #6	Current cholecystitis <del>or gallstones (identified by hepatic imaging)</del>	Current cholecystitis or evidence of current biliary obstruction due to gallstones. Asymptomatic gallstones that are not considered a safety risk in the opinion of the Investigator might be acceptable subject to discussion and agreement with the Medical Monitor

Section	Original Text (Version 3)	Revised Text (Version 4)
8.3. Subject Exclusion Criteria, Exclusion Criterion #10	Known Gilbert's syndrome or elevations in unconjugated (indirect) bilirubin >ULN	Known Gilbert's syndrome or history of elevations in unconjugated (indirect) bilirubin >ULN or unconjugated (indirect) bilirubin >ULN at Screening
12.2.5 Laboratory Assessments	<del>Lp(a)</del>	
Appendix A	<del>Lp(a)</del>	
Appendix A	<del>Samples will be assessed for the presence/absence of Lipoprotein X</del>	

## **APPENDIX J. PROTOCOL VERSION 5 – SUMMARY OF CHANGES**

**Background:** Protocol 747-207 has been prepared as a Phase 2 trial to evaluate the potential clinical benefit of obeticholic acid (OCA) in PSC.

**Rationale:** Version 5 of the protocol includes changes to clarify eligibility inclusion criterion #3 and #9, investigational product storage instructions, clarification for titration adjustments, and clarification for summarizing ECG results. The intention for inclusion criterion #3 is to define the evidence required for diagnosis of PSC, which is, as already stated in inclusion criterion #3, by cholangiography diagnosed at any point in time. The requirement for a mandatory 12-month cholangiogram to diagnose PSC was included in error in the previous version. Inclusion criterion #9 is changed to provide correct examples of barrier methods in the protocol.

**Summary of Changes:** The following revisions were made to Protocol Version 4 in Protocol Version 5. (Note: Deletions are crossed out and additions are indicated in bold font.) Minor grammatical changes are not detailed unless included with other changes (eg, capitalizations, punctuation).

Section	Original Text (Version 4)	Revised Text (Version 5)
Title Page	Original Version: 06 June 2014 Version 2: 24 September 2014 Version 3: 26 August 2015 Version 4: 08 February 2016	Version 5: 18 March 2016
Synopsis, Methodology	Doses of OCA should be titrated as follows, unless clinically indicated: 1.5 mg to 3 mg, 3 mg to 5 mg, and 5 mg to 10 mg.	Doses of OCA should be titrated as follows, unless clinically indicated: 1.5 mg to 3 mg, 3 mg to 5 mg, and 5 mg to 10 mg. Intermediate doses (eg, 6.5 mg) may be considered as deemed appropriate by the Investigator. Dose should not exceed 10 mg.
Synopsis, Inclusion Criterion #3	3. Must have a diagnosis of PSC (based on cholangiography at any point in time) <del>and must have had a cholangiography within the past 12 months</del>	Must have a diagnosis of PSC (based on cholangiography at any point in time).
Synopsis, Inclusion Criterion #9	• <del>Double</del> -barrier method, ie, (a) condom (male or female) or (b) diaphragm, with spermicide; or	Barrier method, ie, (a) condom (male or female) with spermicide or (b) diaphragm with spermicide; or
Synopsis, Investigational Product, Dosage and Mode of Administration	LTSE Phase: All subjects will receive open-label OCA at a starting dose that is dependent upon their dose at completion of DB phase, as well as safety and tolerability. Doses may be 1.5 mg, 3 mg, 5 mg, or 10 mg, ie, 1 or 2 tablets, once daily.	LTSE Phase: All subjects will receive open-label OCA at a starting dose that is dependent upon their dose at completion of DB phase, as well as safety and tolerability. Doses may be 1.5 mg, 3 mg, 5 mg, or 10 mg, ie, 1 or 2 tablets, once daily. Intermediate doses (eg, 6.5 mg) may be considered as deemed appropriate by the Investigator. Dose should not exceed 10 mg.
Synopsis, Safety Analyses	Laboratory parameters, vital signs, <del>and electrocardiograms (ECGs)</del> will be summarized by treatment group using descriptive statistics at Baseline	Laboratory parameters and vital signs will be summarized by treatment group using descriptive statistics at Baseline and at each

Section	Original Text (Version 4)	Revised Text (Version 5)
	and at each scheduled post-Baseline visit. The change from Baseline will also be summarized.	scheduled post-Baseline visit. The change from Baseline will also be summarized. Electrocardiograms (ECGs) will be summarized by treatment group using frequency at each visit. The shift from baseline will also be summarized.
7.4.2, LTSE Phase	...Doses of OCA should be titrated as follows, unless clinically indicated: 1.5 mg to 3 mg, 3 mg to 5 mg, and 5 mg to 10 mg.	Doses of OCA should be titrated as follows, unless clinically indicated: 1.5 mg to 3 mg, 3 mg to 5 mg, and 5 mg to 10 mg. Intermediate doses (eg, 6.5 mg) may be considered as deemed appropriate by the Investigator. Dose should not exceed 10 mg.
8.2 Subject Inclusion Criteria, Inclusion Criterion #3	3. Must have a diagnosis of PSC (based on cholangiography at any point in time) <del>and must have had a cholangiography within the past 12 months</del>	Must have a diagnosis of PSC (based on cholangiography at any point in time).
8.2 Subject Inclusion Criteria, Inclusion Criterion #9	• <del>Double</del> barrier method, ie, (a) condom (male or female) or (b) diaphragm, with spermicide; or	Barrier method, ie, (a) condom (male or female) with spermicide or (b) diaphragm with spermicide; or
10.3 Investigational Product Storage	Investigational product should be stored in the containers in which they are received from the Sponsor's supplier, <del>at controlled room temperature, and protected from excess humidity.</del>	The investigational product should be stored in the containers in which it is received from the Sponsor's supplier, at 15°C to 25°C.
12.2.4, Electrocardiogram	These ECGs must be clearly labeled with the <del>subject's</del> initials , Subject ID number, date and time.	These ECGs must be clearly labeled with the Subject ID number, date and time.
13.5.3, Additional Safety Analyses	Additional safety assessments include vital signs and ECGs. Vital signs <del>and ECGs</del> will be summarized by treatment group using descriptive statistics at Baseline and at each scheduled post-Baseline visit. The change from Baseline will also be summarized.	Additional safety assessments include vital signs and ECGs. Vital signs will be summarized by treatment group using descriptive statistics at Baseline and at each scheduled post-Baseline visit. The change from Baseline will also be summarized. ECGs will be summarized by treatment group using frequency at each

---

Section	Original Text (Version 4)	Revised Text (Version 5)
		visit. The shift from baseline will also be summarized.

|---------------------------------|---|
| DCA | deoxycholic acid |
| DOB | date of birth |
| DOIC | date of informed consent |
| eCRFs | electronic case report forms |
| ECG | Electrocardiogram |
| eCRF | electronic case report form |
| ELF | enhanced liver fibrosis |
| eq | equivalents |
| ERCP | endoscopic retrograde cholangiopancreatography |
| FGF-19 | fibroblast growth factor-19 |
| FXR | farnesoid X receptor |
| g | gram(s) |
| GGT | gamma-glutamyl transferase |
| GI | Gastrointestinal |
| Glyco-CA | glycine 6 α -ethyl cholic acid |
| Glyco-CDCA | glycine 6 α -ethyl chenodeoxycholic acid |
| Glyco-DCA | glycine 6 α -ethyl deoxycholic acid |
| Glyco-OCA | glycine 6 α -ethyl chenodeoxycholic acid |
| Glyco-LCA | glycine 6 α -ethyl lithocholic acid |
| Glyco-UDCA | glycine 6 α -ethyl ursodeoxycholic acid |
| H | High |
| HA | hyaluronic acid |
| IBD | Inflammatory bowel disease |
| ICF | informed consent form |
| ICH | International Conference on Harmonization |
| IgA | Immunoglobulin A |
| IgG4 | Immunoglobulin G4 |
| IgM | Immunoglobulin M |
| IL | interleukin |
| INR | international normalized ratio |
| in | inch(es) |
| ITT | Intent-to-treat |

| Abbreviation or Specialist Term | Explanation |
|---------------------------------|---|
| kg | kilogram(s) |
| KM | Kaplan-Meier |
| L | low |
| lb | pound(s) |
| LCA | lithocholate acid |
| LLN | lower limit(s) of normal |
| LLQ | lower limit of quantitation |
| ln | natural logarithm |
| LOCF | last observation carried forward |
| LS | least-square |
| LTSE | long-term safety extension |
| MedDRA | Medical Dictionary for Regulatory Activities |
| mg | milligram(s) |
| mL | milliliter |
| MRCP | magnetic resonance cholangiopancreatography |
| MW | molecular weight |
| ng | nanogram |
| NMR | nuclear magnetic resonance |
| OCA | obeticholic acid |
| ODS | output delivery system |
| P3NP | procollagen-3 N-terminal peptide |
| PD | pharmacodynamic |
| PK | pharmacokinetic(s) |
| PSC | primary sclerosing cholangitis |
| SAE | serious adverse event |
| SAP | statistical analysis plan |
| SD | standard deviation |
| SE | standard error |
| SEM | standard error of mean |
| SI | international system of units |
| tauro-CA | taurine 6 α -ethyl cholic acid |
| tauro-CDCA | taurine 6 α -ethyl chenodeoxycholic acid |

| Abbreviation or Specialist Term | Explanation |
|---------------------------------|--|
| tauro-DCA | taurine 6 α -ethyl deoxycholic acid |
| tauro-LCA | taurine 6 α -ethyl lithocholic acid |
| tauro-OCA | taurine 6 α -ethyl chenodeoxycholic acid |
| tauro-UDCA | taurine 6 α -ethyl ursodeoxycholic acid |
| TE | transient elastography |
| TEAE | treatment-emergent adverse event |
| TGF- β | transforming growth factor-beta |
| TIMP-1 | tissue inhibitor of metalloproteinase 1 |
| t_{\max} | time to reach C_{\max} |
| TNF- α | tumor necrosis factor alpha |
| UC | ulcerative colitis |
| UDCA | ursodeoxycholic acid |
| ULN | upper limit(s) of normal |
| VAS | visual analogue scale |
| W12C | Week 12 Completers |
| W24C | Week 24 Completers |
| WADD | Weighted average daily dose |
| WHODDE | World Health Organization Drug Dictionary Enhanced |

1. INTRODUCTION

This document outlines the statistical methods to be implemented during the analyses of the double-blind (DB) phase data collected within the scope of Intercept Pharmaceuticals, Inc. (henceforth referred to as Intercept or the Sponsor) Protocol 747-207 (A Phase 2, Randomized, Double-Blind, Placebo-Controlled, Dose-Finding, Clinical Trial Evaluating the Efficacy and Safety of Obeticholic Acid in Subjects with Primary Sclerosing Cholangitis). The purpose of this plan is to provide specific guidelines from which the analyses will proceed. Any deviations from these guidelines will be documented in the clinical study report (CSR). The scope of this plan includes the detailed specifications of the statistical analyses for the DB phase only. A separate statistical analysis plan (SAP) will be written for the long-term safety extension (LTSE) phase of the study. The analyses described in this plan are considered a priori, in that they have been defined prior to database lock of the DB phase. Post hoc analyses will be labeled as such on the outputs and identified in the CSR. Further details about study design and procedures can be found in the protocol.

2. STUDY OBJECTIVES

The primary objective of the DB phase is to evaluate the effects of obeticholic acid (OCA) on the following in subjects with primary sclerosing cholangitis (PSC):

- Serum alkaline phosphatase (ALP)
- Safety

The secondary objectives are to evaluate the effects of OCA on the following in subjects with PSC:

- Hepatic biochemistry and indices of function
- Markers of:
 - Hepatic fibrosis and gastrointestinal (GI) inflammation and disease
 - Farnesoid X receptor (FXR) activity
 - Inflammatory bowel disease (IBD)
- Pharmacokinetics (PK) of OCA and Pharmacodynamic (PD) bile acids
- Exposure response of total OCA (OCA and its conjugates) to biomarkers (eg, ALP and bile acids)
- Long-term efficacy and safety of OCA
- Disease-specific symptoms

3. STUDY DESIGN AND PLAN

This is a Phase 2, randomized, double-blind, placebo-controlled, dose-finding evaluation of the efficacy and safety of OCA in subjects with PSC. The trial design is shown in [Figure 1](#). Approximately 75 subjects who provide written informed consent and meet all of the inclusion

and none of the exclusion criteria will be randomized to 1 of 3 treatment groups as follows: 1.5 mg titrating to 3 mg OCA, 5 mg titrating to 10 mg OCA, or placebo in a 1:1:1 ratio. Subjects will administer investigational product orally, once daily for 2 consecutive 12-week periods. Randomization will be stratified by the presence or absence of concomitant UDCA use and total bilirubin level ($\leq 1.5 \times \text{ULN}$ or $> 1.5 \times \text{ULN}$ but $< 2.5 \times \text{ULN}$). No more than 50% of subjects randomized will be administering UDCA at the time of randomization.

[figure not shown]
For the first 12 weeks after randomization, the subject's dose will be 1.5 mg OCA, 5 mg OCA, or placebo. After 12 weeks, the subject's dose will be titrated – 1.5 mg OCA titrating to 3 mg OCA and 5 mg OCA titrating to 10 mg OCA – and DB treatment will continue for a further 12 weeks at that dose.

Subjects will have a screening period of up to 30 days prior to Randomization/Day 0. Subjects will attend on site clinic visits at Weeks 2, 6, 12, 14, 18, and 24. The final visit during the DB phase will occur at Week 24, after which subjects will be asked to reconfirm their consent for participation in the LTSE phase (a further 24 months).

Upon a subject's completion of the DB phase, the trial blind will be broken in order to assign the starting OCA dose for the LTSE phase. It is intended that subjects will commence treatment at 5 mg OCA, except those subjects who completed treatment in the DB phase with 10 mg OCA who will continue at 10 mg OCA unless safety and tolerability warrant a dose reduction to 5 mg. The titration schedule and options for the LTSE phase are detailed in the protocol.

The overall study duration is up to 32 months, including up to a 30-day Screening period, 6 month DB period, followed by a 24-month open-label LTSE period, and a 1-month follow-up period. The LTSE may be extended as determined by the sponsor via protocol amendment and regulatory and Institutional Review Board/Independent Ethics Committee review and approval.

Figure 1: Study Design Schematic

4. DETERMINATION OF SAMPLE SIZE

A sample size of 25 subjects per treatment group, a total of 75 subjects, will provide at least 90% power to detect a treatment difference for change in ALP assuming 20% dropout and the mean absolute change in ALP for OCA and placebo treatment groups are approximately -20 and -5, respectively, with a pooled standard deviation of 16, based on a 2-sided independent 2-group t-test at an alpha level of 0.05.

In protocol Version 2, dated 24 Sep 2014, the sample size section was updated to reflect absolute change from percent change which was used in protocol Version 1, dated 06 June 2014. In the update, the percentage symbols were not removed. The percentage symbols have been removed in this section of the SAP, in order to accurately reflect what is used in the sample size calculation.

5. STUDY ENDPOINTS

5.1. Primary Endpoints

5.1.1. Primary Efficacy Endpoints

The primary efficacy endpoint is the Week 24 change from Baseline in ALP.

5.2. Secondary Endpoints

As defined in the protocol the secondary endpoints are ALP response rates, indices of hepatic function and GI inflammation, hepatic biochemistry, hepatic inflammation and fibrosis, PK, PD bile acids, and disease specific symptoms. The secondary efficacy endpoints of the DB phase are described below.

5.2.1. ALP Response Rates

The following ALP response rates will be summarized.

- ALP response, defined as ALP value $<1.5 \times$ upper limit of normal, will be evaluated at Baseline and all DB post-Baseline visits
- Percentage change from Baseline $\geq 10\%$, $\geq 15\%$, $\geq 20\%$, $\geq 25\%$, $\geq 30\%$, $\geq 35\%$, and $\geq 40\%$ will be evaluated at all DB post-Baseline visits

5.2.2. Hepatic Biochemistry and Indices of Hepatic Function

The following laboratory parameters will be summarized for hepatic biochemistry and indices of hepatic function: ALP, albumin, alanine transaminase (ALT), aspartate aminotransferase (AST), total bilirubin, direct bilirubin, gamma-glutamyl transferase (GGT), international normalized ratio (INR).

- Observed values, change from Baseline, and percentage change from Baseline will be evaluated at each DB post-Baseline visit

5.2.3. Markers of Hepatic Inflammation and Fibrosis

The following laboratory parameters will be summarized for markers of hepatic inflammation and fibrosis: calprotectin, C-reactive protein (CRP), Cytokeratin-18 (CK-18), Immunoglobulin A (IgA), Immunoglobulin G4 (IgG4), Immunoglobulin M (IgM), Interleukin-6 (IL-6), Interleukin-12 (IL-12), Interleukin-23 (IL-23), Transforming growth factor-beta (TGF- β), Tumor necrosis factor-alpha (TNF- α); and for measures of hepatic stiffness measurements obtained via Transient elastography (TE) at participating sites; and enhanced liver fibrosis (ELF) measures of hyaluronic acid (HA), procollagen-3 N-terminal peptide (P3NP), tissue inhibitor of metalloproteinase 1 (TIMP-1).

- Observed values, change from Baseline, and percentage change from Baseline will be evaluated at each DB post-Baseline visit

5.2.4. FXR Activity

FXR activity will be assessed by measuring fibroblast growth factor-19 (FGF-19).

- Observed values, change from Baseline, and percentage change from Baseline will be evaluated at each DB post-Baseline visit

5.2.5. Pharmacokinetic Endpoints

PK parameters will be estimated for plasma OCA (parent) and its conjugates (glycine 6 α -ethyl chenodeoxycholic acid (glyco-OCA) and taurine 6 α -ethyl chenodeoxycholic acid (tauro-OCA), total OCA, and potentially other conjugates or metabolites not yet identified. PK analyses will utilize non-compartmental methods.

The values will be summarized by active treatment group using descriptive statistics. Only samples that have a confirmed fasting of approximately 8 hours or more before their visit will be included in the analysis.

- The PK endpoints include the Week 12 and Week 24 plasma concentrations at all collection time points, plasma PK parameters; maximum plasma concentration (C_{max}), time to reach C_{max} (t_{max}), and area under the concentration-time curve from hour 0 to last sampling time (hour 6) (AUC_{0-6}) at steady-state.

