**6.4. Dose Adjustment Criteria and Dose Titration****6.4.1. Double-Blind Phase**

Following randomization, subjects will administer the assigned, blinded treatment once daily for 12 weeks.

After 12 weeks, the subject's dose will be titrated as follows, providing there are no limiting safety or tolerability concerns in the opinion of the Investigator, while maintaining the trial blind: the 1.5 mg OCA treatment group will titrate to 3 mg, the 5 mg OCA treatment group will titrate to 10 mg OCA, and the placebo group will remain on placebo. DB treatment will continue for a further 12 weeks at that dose.

Any subjects whose dose is not titrated, due to safety or tolerability concerns, will remain on their starting treatment (1.5 mg OCA, 5 mg OCA, or placebo) for the remainder of the DB phase to Week 24.

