### 8.2.2. Bile Acid Sequestrants

While systemic or enteral therapy for pruritus is an exclusion criterion at trial entry, the treatment of pruritus during the trial is permitted if required.

Bile acid sequestrants (BAS), aluminium hydroxide, or smectite-containing antacids should be administered at least 4 hours apart from investigational product (ie, they should be used 4 hours prior to or 4 hours after investigational product administration).

In addition, BAS, aluminium hydroxide, or smectite-containing antacids should be administered at least 4 hours apart from UDCA (ie, they should be used 4 hours prior to or 4 hours after UDCA administration).

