#### **9.4.3. Overdose**

The maximum dose of OCA that has been given to humans is 500 mg as a single dose and 250 mg as a multiple dose. Reversible increases in aminotransferases were seen in most of the healthy volunteers who took 250 mg OCA. If overdose occurs in a subject enrolled in the trial, general medical supportive measures should be provided, including observation and follow-up (eg, serum chemistry) as appropriate. Due to the extensive enterohepatic recirculation of OCA it is likely that it will take several days before blood (and organ) concentrations of the drug will decrease. Treatment with cholestyramine (eg, Questran™), colestevlam (eg, Welcol™) and other BAS is recommended given that they should bind and eliminate the drug in feces. The Sponsor should be notified immediately in the event of a significant overdose.

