#### 11.1.3.1. Severity of Pruritus (as an AE)

Pruritus was the most common AE seen in the Phase 2 and Phase 3 PBC trials and thus may occur in this trial. Subjects experiencing, or who have experienced within  $\leq 3$  months of

Screening, pruritus requiring systemic or enteral treatment are excluded from participating in this trial.

To ensure consistency in reporting, the following guidelines for assessing severity of pruritus should be used both for AE reporting and during pretreatment assessment. As pruritus is a subjective symptom, clinical judgment should be used to determine its severity and management. Subjects who experience a treatment emergent AE of severe pruritus should not be titrated to a higher dose.

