- Dose frequency modification: Less frequent dosing of investigational product (eg, on alternate days) may be tried, after which subjects may return to their original daily dose, if and as tolerated.
- Drug holiday: A drug holiday is defined as an Investigator ‘prescribed’ complete interruption of dosing for 1 or more consecutive days (ie, non-daily dosing does not constitute a drug holiday). For subjects with severe pruritus, instruct the subject to stop taking investigational product until the pruritus subsides to an acceptable level at which time it should be restarted (likely, on a modified, alternate day dosing schedule). Details of drug holidays and/or nondaily dosing regimens should be recorded in the CRF. Such cases should be discussed with the Medical Monitor.
- Other therapies may be tried as deemed clinically appropriate.

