7.4. Per Protocol Population

All randomized subjects without major protocol deviations that potentially affect the efficacy of the study drug will be included in the per protocol population. Subjects who are in the study through Week 12 who do not up titrate their dose of IP will be excluded from the per protocol population. Treatment assignment will be based on the randomized treatment.

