7.6. Pharmacokinetic (PK) Population

The PK Population will include all OCA subjects who consent to participate in the PK assessments and have at least one confirmed fasted analyzable sample. Subjects must have been fasting for approximately 8 hours before the visit and must not have any major protocol deviations that potentially affect exposure levels. The PK Population will be used for the OCA PK and pharmacodynamic (PD) analyses.

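### Week 24 PK summaries by treatment group mix two dose levels within an arm, because nothing separates subjects who stay on the starting dose or dose less often than daily

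*SAP*

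**What the plan says.** SAP Section 5.2.5 names the Week 12 and Week 24 plasma concentrations, Cmax, tmax and AUC0-6 at steady state as the PK endpoints, and adds: "The values will be summarized by active treatment group using descriptive statistics". Sections 9.2.4.1 and 9.2.4.2 prescribe arithmetic and geometric summaries and mean and median concentration plots, with no division by dose taken. Appendix A lists one Week 12/24 concentration table and one Week 12/24 parameter table.

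The protocol allows departures from the target regimen. Section 6.4.1: "Any subjects whose dose is not titrated, due to safety or tolerability concerns, will remain on their starting treatment". Section 11.1.3.1: "Subjects who experience a treatment emergent AE of severe pruritus should not be titrated to a higher dose". For significant pruritus, the same section adds: "Less frequent dosing of investigational product (eg, on alternate days) may be tried"; it also describes drug holidays.

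Entry to the PK population (SAP Section 7.6) needs consent, a confirmed fasted sample that can be analysed, and a subject who "must not have any major protocol deviations that potentially affect exposure levels". The Per Protocol population (Section 7.4) has an additional rule: subjects who reach Week 12 and "who do not up titrate their dose of IP will be excluded from the per protocol population".

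**The concern.** The trial is dose-finding, and PK is a secondary objective in the protocol. Each active arm doubles its dose at Week 12, so a reader will naturally use the Week 12 and Week 24 columns to see what doubling does to exposure. If some Week 24 profiles in an arm were taken on the starting dose, the arm average describes neither dose. The apparent increase is diluted, and doubling can look less than dose-proportional for that reason alone. The subjects held back are not a random subset: they stay on the lower dose because of safety or tolerability. A profile taken on alternate-day dosing likewise does not represent once-daily steady state.

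**Working it through.** The plan states no figure to reproduce. The check is a reading of the rules followed by an illustration.

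**Can an off-target profile reach the Week 24 summary?**

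1. Protocol Sections 6.4.1 and 11.1.3.1 make non-titration and non-daily dosing permitted conduct. They are not in themselves protocol deviations.
2. Protocol Section 10.5 has each PK participant take their own allocated product on the sampling day. A non-titrated subject is therefore sampled on 1.5 or 5 mg at Week 24.
3. SAP Section 7.6 removes only major deviations affecting exposure. Section 7.4 shows that this is not enough: it has a major-deviation rule and still needs a separate sentence to drop non-titrators. Section 7.6 has no such sentence.
4. SAP Section 10.1.1 counts subjects who did not titrate, had alternate dosing or had a reduced dose, but only for the exposure summary. The PK sections do not use these counts.

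So the answer is yes.

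**How far could the averages move?**

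From the documents: full titration doubles the dose in both arms (1.5 to 3 mg, 5 to 10 mg). Assumed: exposure proportional to dose, the same PK subjects sampled at both visits, and a share p not titrated. Let r be the exposure per mg of non-titrators relative to titrators. The unit is the titrators' geometric mean at the starting dose.

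- Week 12 by-arm geometric mean = r^p
- Week 24 by-arm geometric mean = 2^(1−p) × r^p
- Ratio = 2^(1−p), against 2.00 if all titrate; r cancels
- Week 24 value relative to all subjects on target = 2^(−p)
- Mean nominal dose at Week 24 = target × (1 − p/2)

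| p | Week 24/Week 12 ratio | Relative to all on target | Mean nominal dose, 5 to 10 mg arm | Mean nominal dose, 1.5 to 3 mg arm |
|---|---|---|---|---|
| 10% | 1.87 | 0.93 | 9.5 mg | 2.85 mg |
| 20% | 1.74 | 0.87 | 9.0 mg | 2.7 mg |
| 30% | 1.62 | 0.81 | 8.5 mg | 2.55 mg |

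**Spread.** Mixing doses adds p(1−p)(ln(2/r))² to the log-variance. The same subjects all on target would add p(1−p)(ln r)². The first term is larger only if r < √2 = 1.41. At r = 1 and p = 20%, the mixing component of the log-scale SD is ln 2 × √(0.2 × 0.8) = 0.28. Above r = 1.41, mixing lowers the spread.

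**Would actual-dose columns recover 2.00?** Not alone. The Week 24 10 mg column holds titrators only, while the Week 12 5 mg column holds everyone, so their ratio is 2 × r^(−p). With p = 20% and an assumed r = 1.5, that is 2 × 1.5^(−0.2) = 1.84. A within-subject ratio in titrated subjects gives 2.00 under proportionality, whatever r is.

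The effect of alternate-day dosing or of a sequestrant on AUC0-6 cannot be computed from the documents.

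**The case against.** **The wording is open.** The SAP does not define active treatment group, and Section 7.6, unlike the other populations, gives no treatment-assignment rule. Section 9.2.4.3 also leaves the final choice of PK subjects and samples to a decision before database lock. Grouping by actual dose is therefore not ruled out. This stands in part, but grouping by arm is the natural reading, and the pre-lock decision carries no dose or frequency criterion.

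**A reader might infer that a subject on 5 mg will be reported under a 10 mg label.** The documents do not go that far. The 3 mg and 10 mg arm labels come from SAP Sections 6.2.7 and 9.1, which concern efficacy. The PK table titles carry no dose.

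**A reader might infer that dose selection is compromised.** Protocol Sections 10.5 and 12.4 give that purpose to the exposure-response analysis. SAP Section 9.2.5 carries it out with scatter plots in which each subject appears at their own measured AUC0-6. Individual profiles and subject listings are also planned, and SAP Section 9.2.4 calls the PK analyses exploratory. This objection stands and confines the harm to descriptive summaries.

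**A reader might take the sequestrant uptake in the Phase 3 PBC trial (20% and 27% in the OCA arms, Protocol Section 11.1.3.1) as the scale of non-titration.** It measures a different event in a different disease. Protocol Section 7.4.2 calls pruritus less common in PSC, and exclusion criterion 12 bars recently treated pruritus.

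**Sequestrants are a weaker case.** Protocol Section 8.2.2 says "the treatment of pruritus during the trial is permitted if required" and requires sequestrants to be taken at least 4 hours apart from investigational product. Users still take their assigned dose. The remark that sequestrants are recommended "given that they should bind and eliminate the drug in feces" is overdose advice and shows no effect under spaced dosing. What remains is heterogeneity worth flagging.

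**A by-arm summary is a legitimate description of a randomised titration regimen.** That stands, and is a reason to keep it alongside.

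**Conclusion.** The point holds within narrow limits. As written, the Week 24 concentration, Cmax and AUC0-6 tables and the mean and median plots can mix two dose levels, and once-daily with less frequent dosing, within an arm. The scatter plots, the listings and the primary ALP test are not touched.

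The tabulated 7%, 13% and 19% shortfalls are illustrations. They rest on assumed dose proportionality, an assumed non-titration share and the same subjects being sampled at both visits. If nobody stays on the starting dose, the non-titration dilution is zero. A claim that variability is inflated is not supported, because its direction depends on whether non-titrators have more than about 1.41 times the exposure per mg.

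**What to change.** In SAP Sections 5.2.5, 9.2.4.1 and 9.2.4.2:

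- Summarise Week 24 PK by the dose and frequency being taken at the sampling visit, with non-titrated subjects in their actual-dose column. Dose-normalised values are an alternative.
- List profiles taken on non-daily dosing or just after a drug holiday separately from the once-daily steady-state summary.
- Base any Week 12 to Week 24 dose comparison on within-subject ratios in titrated subjects.
- Keep the by-arm table, with the number not titrated in a footnote.
- Flag sequestrant users at the visit.

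The cost is SAP wording and regrouped tables. No new data are needed: the titration decision is entered in the IWRS at Week 12, and drug holidays, non-daily regimens and concomitant drugs are recorded in the CRF. The downsides are small cells, since PK sampling is optional at selected sites in arms of about 25, and columns that are not randomised comparisons, since those who titrate are selected on tolerability. The SAP should state both.
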